4.2. Sample Size

The sample size (N) of up to 68 for this study is based on clinical and practical considerations and not on a formal statistical power calculation. The sample size is considered sufficient to adequately assess the safety, PK, and PD profiles of MEDI2452 (PB2452) and the PK and PD profiles of ticagrelor.

4.3. Randomization, Stratification, and Blinding

Randomization to MEDI2452 (PB2452) or placebo within each one of the ten cohorts will be based on a randomization schedule prepared by PPD before the start of the study using SAS® software. The randomization scheme within each cohort is specified in [Table 3-1](#). There will be no stratification factors in the randomization.

This is a double-blind study. Neither the subjects nor the investigator will be aware of the treatment assignment. Blinding will be maintained throughout the study by use of active and placebo dosage forms of similar appearance once prepared. To maintain the blind, only designated pharmacy staff at the clinical site will have access to the randomization code and will prepare each dose for each subject. The PK and PD samples will be shipped to the designated laboratories who are only responsible for analyzing the PK and PD samples and will not be involved in any other study activities. In order to prepare preliminary summaries of safety, PK, and/or PD data as needed to make timely decisions regarding adjustment of study procedures, dosing regimens, or potentially early termination of the study, certain designated staff at PhaseBio and PPD who are not involved in the study design or conduct may be unblinded during the conduct of the study (study director, a single biostatistician, bioanalytical scientist, and programming team) before data is more generally unblinded. These summaries will not reveal individual subjects' treatment assignments. All other members of PhaseBio research and development and members from PPD will remain blinded. Access to the randomization code will be strictly controlled according to PPD and PhaseBio standard operating procedures.

The scheduled unblinding event to all study members will occur after the database is locked (hard-locked).

4.4. Breaking the Blind

A subject may be unblinded in the event of a dose limiting toxicity (DLT), serious AE (SAE), or other event, or if there is a medical emergency where the identity of the drug must be known to properly treat a subject. A cohort may be unblinded to determine if dose escalation to the next dose level will terminate. If a subject becomes seriously ill during the study, the blind will be broken only if knowledge of the administered study drug will affect that subject's treatment options. In the event of a medical emergency requiring identification of the study drug administered to an individual subject, the investigator will make every attempt to contact the medical monitor to explain the need for opening the code within 24 hours of opening the code. The investigator will be responsible for documenting the time, date, reason for the code break, and the names of the personnel involved.

4.5. Replacements

At the discretion of the investigator after consultation with the sponsor, any subject who withdraws before completing the study, for reasons other than a DLT may be replaced. Any replacement subject will be assigned to receive the same treatment as the subject he or she is replacing.

4.6. Repeated/Unscheduled Measurements

For safety summary tables summarized by time point, excluding baseline, if there are repeated measurements for a subject at a scheduled time point, the original scheduled measurement at that time point will be used in the summary tables.

Unscheduled results, i.e. results that are not from a scheduled event or repeated measurements for a scheduled event, will not be included in the summary tables except for determining baseline, but will be presented in data listings.

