4.1. General Data Presentation Rules

All data will be provided in individual by-subject listings.

Data from subjects excluded from an analysis population will be presented in the data listings but not included in the calculation of summary statistics.

Data from subjects receiving placebo will be pooled across cohorts for all presentations.

Unless otherwise noted, the following treatment groups will be used in summaries:

- 100 mg PB2452 (C1)
- 300 mg PB2452 (C2)
- 1000 mg PB2452 (C3)
- Placebo C1-C3
- 1000 mg PB2452 (C4)
- 3000 mg PB2452 (C5)
- 9000 mg PB2452 (C6)
- Placebo C4-C6
- 18000 mg PB2452 (C7)
- 18000 mg PB2452 (C8)
- 18000 mg PB2452 (C9)

- 18000 mg PB2452 (C10)
- Placebo C7-C10
- All Placebo (for safety summaries only)
- All PB2452 (for safety summaries only)
- All subjects

where 'C' means 'Cohort'.

Demographic data, baseline characteristics, adverse events (AEs), laboratory tests, vital signs, 12-lead electrocardiogram (ECG) measurements, and subject disposition will be summarized descriptively.

Unless otherwise noted, the summary of the continuous variables will include the number of subjects with non-missing data (n), mean, standard deviation (SD), median, minimum, and maximum. Categorical variables will be summarized descriptively by their counts and associated percentages. Percentages will be calculated using the number of subjects within a summary group as the denominator.

Minimum and maximum values will be presented as the same precision as the original value. Means and medians will be presented as 1 decimal place greater than the precision of the original value. Standard deviations will be presented as 2 decimal places greater than the precision of the original value. Percentages for summarizing categorical data will be presented with 1 decimal place. If the percentage value is less than 0.1, then "<0.1" will be displayed.

Unless specified otherwise, baseline for safety analyses is defined as the last non-missing measurement (including repeated and unscheduled measurements) prior to the first study drug administration; baseline for PD analyses is defined as the last non-missing measurement (including repeated and unscheduled measurements) prior to the first ticagrelor administration.

Listings will be sorted by treatment group and subject identifier.

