8.1.6. Dose Limiting Toxicities

The SRC will review all AEs and all laboratory and ECG abnormalities according to CTCAE v5 to determine whether a DLT has been identified in a subject who is confirmed to have received MEDI2452 (PB2452). If the SRC determines that an AE is related to

administration of ticagrelor (Cohorts 4-10), or another confirmed cause, the AE will not be considered a DLT.

The SRC will provide an external spreadsheet which contains all DLT events and this external spreadsheet will be used in the summaries and listings.

Definitions for DLT are described below:

1. A DLT is defined as any AE that is assessed as grade 2 or higher based on the CTCAE v5 grading scale and has occurred in a subject confirmed to have received MEDI2452 (PB2452).
2. A DLT is defined as any grade 2 or higher laboratory abnormality (outside the clinical laboratory normal reference range) that occurs in a subject confirmed to have received MEDI2452 (PB2452). [Note: For a grade 2 electrolyte abnormality that spontaneously resolves to \leq grade 1 (without intervention) within 24 hours, the SRC may decide to exempt the laboratory abnormality from being considered a DLT].
3. A DLT is defined as any TEAE that leads to study withdrawal of a subject confirmed to have received MEDI2452 (PB2452).

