8.2. Clinical Laboratory Evaluations

Blood samples for laboratory safety tests (hematology, coagulation and serum chemistry) and urine samples for urinalysis will be collected at Screening, Day -3 (Cohorts 4 through 10 only), Day -1 (Cohorts 1 through 3 only), Day 3 (Cohorts 1 through 8 and 10 only), Day 4 (Cohort 9 only if a 6th dose of ticagrelor was given on Day 2), Day 7, and Day 28/EOS.

Serology testing will be performed at Screening.

Urine drug, alcohol screen, and Hemoglobin A1C for diabetic patients, will be performed at Screening, Day -3 (Cohorts 4 through 10 only), and Day -1 (Cohorts 1 through 3 only).

Serum pregnancy test for female subjects will be performed at Screening, Day -3 (Cohorts 4 through 10 only), Day -1 (Cohorts 1 through 3 only), and Day 28/EOS.

Stool occult blood test will be performed at Screening for Cohort 10 only.

The following clinical laboratory assessments will be performed:

Hematology: Hematocrit, hemoglobin, mean corpuscular hemoglobin, mean corpuscular hemoglobin concentration, mean corpuscular volume, platelet count, red blood cell count, and total and differential leukocyte count

Coagulation: Activated partial thromboplastin time, international normalized ratio, partial thromboplastin time, and prothrombin time

Serum Chemistry: Alanine aminotransferase, albumin, alkaline phosphatase, aspartate aminotransferase, bicarbonate, bilirubin (total and direct), blood urea nitrogen, calcium, chloride, cholesterol (total, high-density lipoprotein, and calculated low-density lipoprotein), creatine phosphokinase, creatinine, gamma-glutamyltransferase, globulin, glucose, lactate dehydrogenase, magnesium, phosphorus, potassium, sodium, thyroid stimulating hormone (Screening only), total protein, triglycerides, and uric acid

Urinalysis: Appearance, bilirubin, color, glucose, ketones, leukocyte esterase, reflex microscopy (performed if dipstick is positive for protein or blood value of 1+ or greater; and includes bacteria, casts, crystals, epithelial cells, red blood cells, and white blood cells), nitrites, occult blood, pH, protein, specific gravity, turbidity, and urobilinogen

Serology: Hepatitis B surface antigen, hepatitis C virus antibody, and human immunodeficiency virus types 1 and 2 antibodies

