Other analyses: Urine drug screen (amphetamines, barbiturates, benzodiazepines, cannabinoids, cocaine, cotinine, methylenedioxymethamphetamine, opiates, phencyclidine, propoxyphene, and tetrahydrocannabinol), urine alcohol. Follicle-stimulating hormone and serum pregnancy test (human chorionic gonadotropin) will be collected for female subjects.

The investigator will determine whether any of the abnormally high or low results are clinically significant or not clinically significant.

The hematology and coagulation, chemistry, and urinalysis test results will be presented in the data listings sorted by treatment group, subject, laboratory test, and sample collection date/time. Values that are outside of the normal range as well as the clinically significance information will be flagged in the listings. Actual results and change from baseline will be summarized for the safety population. Refer to [Section 4.1](#) for the definition of baseline for this summary. Shift tables will be generated for the safety population.

All other laboratory tests will be presented in a data listing sorted treatment group, subject, laboratory test category, laboratory test, and sample collection date/time.

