8.4. Twelve-Lead Electrocardiogram and Telemetry Monitoring

Triplicate 12-lead ECGs will be obtained after the subject has been in the supine position for at least 10 minutes at Screening, within 1 hour prior to the initiation of the study drug infusion, and at 1 hour, 4 hours, 5 hours, 24 hours, and 48 hours after the initiation of the study drug infusion, and on Day 7 and Day 28/EOS and as indicated by AEs or telemetry findings. Electrocardiogram assessments will include comments on whether the tracings are normal or abnormal, rhythm, presence of arrhythmia or conduction defects, morphology, any evidence of myocardial infarction, or ST-segment, T-Wave, and U-Wave abnormalities. In addition, measurements of the following intervals will be measured and reported: RR interval, PR interval, QRS width, and Fridericia-corrected QT interval (QTcF). The investigator will determine whether any of the 12-lead ECG results are clinically significant or not.

If both QT and RR intervals are not missing, the Bazett's-corrected QT interval (QTcB) measured in msec will be calculated using below formula, where RR interval is measured in msec:

$$\bullet \quad QTcB = \frac{QT}{\sqrt{RR/1000}}$$

If both QT and RR intervals are not missing but QTcF interval is missing in the database, QTcF measured in msec will be calculated using below formula, where RR interval is measured in msec:

$$\bullet \quad QTCF = \frac{QT}{\sqrt[3]{RR/1000}}$$

Electrocardiogram results will be presented in data listing sorted by treatment group, subject, and date/time of assessment. In addition, subjects with outlying QTcF, and QTcB intervals (absolute value > 500 msec, absolute value > 480 msec, absolute value > 450 msec, or increase from baseline value >30 or >60 msec) will be listed in a separate data listing based on the International Council for Harmonisation (ICH) harmonized tripartite guideline E14. A summary table will be presented for maximum QTcF and QTcB intervals (including scheduled and unscheduled assessments) meet the outlying criteria using count and percentage.

Actual results and change from baseline will be summarized for the safety population using the average values of the triplicate ECG assessments at each timepoint. Baseline is defined as the last non-missing average value prior to the first study drug administration.

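### Post-baseline unscheduled laboratory results enter no laboratory summary table and no worst-value shift is planned, so an excursion seen only between scheduled panels is missing from the laboratory change and shift tables

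*SAP*

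**What the plan says.** SAP 4.1 lets off-schedule values set the reference point: "baseline for safety analyses is defined as the last non-missing measurement (including repeated and unscheduled measurements) prior to the first study drug administration". After baseline, SAP 4.6 applies a different rule. Where a scheduled time point has repeated measurements, "the original scheduled measurement at that time point will be used in the summary tables". Unscheduled results "will not be included in the summary tables except for determining baseline"; they are shown in the listings.

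SAP 8.2 fixes the post-dose panels as "Day 3 (Cohorts 1 through 8 and 10 only"), Day 4 for Cohort 9 only if a sixth ticagrelor dose was given, then Day 7 and Day 28 for everyone. It plans summaries of actual values and changes, and adds that "Shift tables will be generated for the safety population". It defines no worst post-baseline value and makes no exception to 4.6. The table list in SAP section 15 matches: Tables 14.3.4.1.1 to 14.3.4.1.3 for values and changes, Tables 14.3.4.2.1 to 14.3.4.2.3 for shifts, and no other laboratory summary.

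For QTc the SAP does make an exception. SAP 8.4 states: "A summary table will be presented for maximum QTcF and QTcB intervals (including scheduled and unscheduled assessments").

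**The concern.** Safety and tolerability is a primary objective of this first-in-human study, and the shift tables are where a reader looks for laboratory change by treatment group. Off-schedule samples are often drawn because something looked abnormal, so leaving them out removes values that are more likely than average to be abnormal. The handling is also uneven. An unscheduled value may define where a subject started but not how far that subject moved, and the SAP admits unscheduled values for the QTc maximum but not for laboratory data. At stake is whether the laboratory tables give a complete summary of the excursions that were observed.

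**Working it through.** No plan figure needs reproducing, because the point turns on a data-handling rule. The check is to follow each kind of post-dose laboratory result to the outputs it can reach.

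**1. Intervals between scheduled panels** (SAP 8.2; dosing on Day 1)

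| Cohorts | Intervals |
|---|---|
| 1 to 8 and 10 | Day 1 to 3: 3 − 1 = 2 days; Day 3 to 7: 7 − 3 = 4 days; Day 7 to 28: 28 − 7 = 21 days, up to 23 with the +2-day window |
| 9, sixth ticagrelor dose given | Day 1 to 4: 3 days; Day 4 to 7: 3 days; then as above |
| 9, no sixth dose | Day 1 to 7: 6 days; then as above |

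A laboratory result dated inside one of these intervals comes from an unscheduled sample. The Cohort 9 rows follow the text of SAP 8.2. SAP Table 3-2, as far as its layout can be read, puts no cohort limit on the Day 3 panel.

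**2. Where each result goes**

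| Result | Change and shift tables | Listings (SAP 8.2) | AE or DLT summaries |
|---|---|---|---|
| Scheduled value | Yes | Yes, flagged | If it qualifies |
| Repeat at a scheduled time | Original used in by-time-point tables; shift tables unclear | Yes, flagged | If it qualifies |
| Unscheduled, between panels | No (SAP 4.6) | Yes, flagged | If it qualifies |

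**3. Repeats.** The rule that keeps the original value covers safety tables summarized by time point. SAP 8.2 does not say whether the shift tables are built that way. The definition of unscheduled results in 4.6 can be read as including repeats or as setting them apart. When an abnormal scheduled value prompts a repeat, keeping the original keeps the abnormal value. Only a repeat worse than its original drops out. Between-panel results are excluded on either reading.

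**4. Are off-schedule samples expected?** Yes. Protocol 3.5.5 allows repeat tests to evaluate laboratory abnormalities and calls for further assessments after a clinically significant change. SAP 8.1.6 allows an exemption for a grade 2 electrolyte abnormality that resolves within 24 hours. With panels at least 2 days apart, that can normally be judged only on extra samples.

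**5. Effect of one affected subject.** Active groups have 3 or 6 subjects (SAP Table 3-1). Suppose one subject is normal at baseline and at every scheduled panel, and out of range only on a sample between Day 3 and Day 7. Under 4.6 the shift table shows 0/3 or 0/6 = 0%. A shift to the worst value shows 1/3 = 33% or 1/6 = 17%. This is an illustration, not an estimate of how often it happens.

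**The case against.** The best defence is that scheduled values in by-visit tables are common practice and that other routes carry the excursions. Listings flag out-of-range and clinically significant values. Protocol 3.5.5 sends clinically significant changes to the AE page, from which they reach the treatment-emergent AE tables. The safety review committee reviews all laboratory abnormalities, and its DLTs feed the Any DLT row of the overall AE table. With so few subjects per cohort, listings can be read subject by subject. The QTc table is tied to ICH E14 and declared as an added analysis in SAP section 12, so it does not oblige the SAP to treat laboratory data the same way.

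Most of this stands, and it limits the point to one missing display. What remains is that the AE route depends on the investigator's judgement of clinical significance, and the DLT route covers only subjects confirmed to have received MEDI2452. An excursion outside both is compared between active and placebo in no table.

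A reader might infer more than the documents support:

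- **That oversight of subjects is impaired.** It is not. The committee's review is not limited to scheduled samples; the gap is in summary reporting.
- **That the DLT row and the shift tables contradict each other.** SAP 8.1.6 says "A DLT is defined as any grade 2 or higher laboratory abnormality", with no limit to scheduled samples, so a subject can be in that row and show no shift. But the row counts adjudicated, graded events on active drug, and the shift tables describe laboratory categories. They need not agree.
- **That the chance of a panel overlapping a short abnormality measures the harm.** That chance describes how sparse the schedule is. If no unscheduled sample is drawn, SAP 4.6 hides nothing and a worst-value table recovers nothing.

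**Conclusion.** The point holds as a narrow reporting gap and is an optional improvement. A laboratory excursion seen only on a sample drawn between scheduled panels appears in no laboratory change or shift table, and no worst-value display makes up for this. The gap concerns mainly between-panel samples; for repeats the SAP is ambiguous and the retained original usually protects the signal.

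The size cannot be stated as a rate. The relevant quantity is the number of subjects whose worst post-dose result is an unscheduled one, and the documents give no basis for it. It could be zero. For any one such subject, the shift-table incidence in an active group changes by 33 or 17 percentage points.

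The conclusion rests on SAP 4.6 applying to the shift tables as written, since 8.2 states no exception, and on the panel schedule in SAP 8.2. The remarks on repeat testing and AE recording come from the protocol dated 01 Feb 2018. The SAP follows Amendment 5 of 03 August 2018, which was not available, so those details may have changed. The exclusion itself is in the SAP and does not depend on them.

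**What to change.** Keep the by-visit rows under SAP 4.6. Add to Tables 14.3.4.2.1 to 14.3.4.2.3 one shift from baseline to worst post-baseline value, by treatment group, using scheduled, repeat and unscheduled results. State in 8.2 that this display is exempt from 4.6, and take the worst high and worst low separately where both directions matter. While editing 4.6, say plainly whether repeats count as unscheduled and whether the existing shift tables are by visit.

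The cost is a few sentences and one extra column set; the results are already collected for the listings. The downside is small: subjects with AEs are sampled more often, so their worst values have more chances to be extreme. Showing the by-visit and worst-value versions together lets the reader see this.

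A count of subjects crossing the liver-test thresholds in protocol 3.4.2.4 should not be added as it stands. Those thresholds come from the February 2018 text and include a judgement that no other explanation exists, which a plain count would not reproduce. If such a count is wanted, tie it to the laboratory criteria in the current amendment.

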4.7. Handling of Missing Data

Subjects with missing data for some summary statistic will not be included in the calculation of that statistic but are eligible for inclusion in any other summary statistic for which they provide data. For the purpose of determining inclusion of AEs in treatment-emergent AE (TEAE) summary tables, incomplete or missing AE onset and end dates will be imputed as follows:

Incomplete or missing onset dates (where UK and UNK indicate unknown or missing day and month, respectively):

- UK-MMM-YYYY: If the month and year are different from the month and year of the dose of study drug, assume 01-MMM-YYYY. If the month and year are the same as the dose of study drug month and year, and the end date (after any imputation) is on or after the dose of study drug, then assume the date of the dose of study drug. If the month and year are the same as the dose of study drug month and year and the end date (after any imputation) is prior to the dose of study drug, then assume the end date for the onset date.
- DD-UNK-YYYY or UK-UNK-YYYY: If the year is different from the year of dose of study drug, assume DD-JAN-YYYY or 01-JAN-YYYY of the onset year, respectively. If the year is the same as the dose of study drug year, and the end date (after any imputation) is on or after the dose of study drug, then assume the date of the dose of study drug. If the year is the same as the dose of study drug, and the end date (after any imputation) is prior to the dose of study drug, then assume the end date for the onset date.
- Missing onset date: If the onset date is completely missing and the end date (after any imputation) is on or after the dose of study drug, then assume the date of the first dose of study drug. If the end date (after any imputation) is prior to the dose of study drug, then assume the end date for the onset date.

Incomplete or missing end dates (where UK and UNK indicate unknown or missing day and month respectively):

- UK-MMM-YYYY: Assume the last day of the month;
- DD-UNK-YYYY or UK-UNK-YYYY: Assume DD-DEC-YYYY or 31-DEC-YYYY, respectively;
- Missing end date: Assume 31-DEC-YYYY, where YYYY is the year of the dose of study drug.

An AE with missing onset time but with an onset date the same as the dosing date of study drug will be classified as treatment-emergent, unless the AE was reported pre-dose with the same or worse intensity or frequency.

Medications with missing start time but with a start date the same as the dosing date of study drug will be considered as being taken on or after the initiation of study drug, unless the electronic case report form (eCRF) question “Was the medication/therapy taken prior to the study” is answered as “Yes” which is considered as being taken prior to the initiation of study drug.

